8.6 Pharmacokinetic Analysis Set

The Pharmacokinetic Analysis Set will include all index subjects who received at least one dose of moxidectin and provided at least one quantifiable post-dose plasma PK concentration.

9 STATISTICAL METHODS OF ANALYSIS

9.1 General Analytic and Reporting Principles

The results of the statistical analyses will be reported using summary tables and figures, with all data reported as listings. All analyses will be performed using SAS Version 9.4 or later.

Data will be summarized in tabular form by dose group in order of ascending dose (moxidectin 8 mg, moxidectin 16 mg, moxidectin 32 mg), placebo and overall subjects.

Summary statistics for continuous variables will consist of the number of non-missing observations (n), mean, standard deviation (SD), minimum, median and maximum, unless specified otherwise. Summary statistics for categorical variables will include the number (count) and percentage of subjects. In general, the percents will be calculated using the denominators for each treatment group within the analysis population being considered. Percentages based on other denominators will be noted. If relevant, tabulations of categorical data will include all categories captured on the eCRF even if no observations in the database appear in those categories. In this situation a '0' will be inserted. For certain categorical variables the number of participants with missing data may also be provided; however, the number missing will not be included in the calculations of percentages.

For proportions, asymptotic Wald confidence intervals (CIs) will be calculated. When the normal approximation may not hold, exact CIs may also be calculated. Confidence intervals based on bootstrapped standard errors (SEs) will be flagged in tables if relevant.

No preliminary rounding will be performed. Any rounding will only occur after analysis for the purposes of data presentation.

For any analyses using a randomized component such as bootstrapped statistics or permutation tests, the randomization seeds used to produce the analysis will be saved and documented to enable the results to be reproducible.

9.1.1 Final Efficacy Analysis at Day 42

After the last subject has completed their Day 42 visit, the efficacy and safety data collected through Day 42 will be cleaned and a frozen/locked snapshot of the data will be made available for analysis. The Day 42 analysis will include the final analysis of the study's primary efficacy endpoint, the Complete Cure rate at Day 28, and other Day 28 exploratory efficacy endpoints. As no further efficacy data is collected beyond Day 28, these efficacy analyses will be considered final even though the study will continue to collect safety data through Week 16. In addition to the Day 28 efficacy data, the Day 42 analysis will also include the analysis of safety through Day 42. PK data, although collected up to and including Day 42, may be analyzed in the Week 16 analysis.

9.1.2 Extended Follow Up at Week 16

The additional safety data collected from Day 42 through Week 16, the extended safety follow up period, will be analyzed after the last subject has completed their Week 16 visit and the study has completed. The Week 16 analysis will be a rerun of selected outputs only where additional information was captured after the Day 42 visit. These additional data may include protocol

CONFIDENTIAL

deviations, disposition (including completions and withdrawals), AEs, concomitant medications, physical examinations, vital signs, and pregnancy testing. For these data, the summary tables may include the Day 42 results from the Day 42 analysis summarized above, the extended follow up at Week 16 results for data collected after the Day 42 visit through Week 16, and a total summary that combines all data from randomization through Week 16. If the PK analysis is not run at Day 42, then the Week 16 outputs will include PK data summaries.

9.2 Multiplicity Adjustments

The three primary efficacy hypotheses to be tested are the comparison of the Day 28 Complete Cure rates (proportions) for each of three moxidectin dose groups to the placebo. As such, statistical significance will be based on a Dunnett adjusted two-tailed alpha level of 0.019 to account for the multiplicity of the three primary efficacy analyses and maintain a FWER of 0.05. For each comparison Wald type 95% CIs incorporating Dunnett's critical value. See Section 9.11.1 for the SE calculation to be used for the 95% CIs.

Other than those specified above, there will be no other multiplicity adjustments.

9.3 Interim Analysis

No interim analyses will be conducted for efficacy. The final analysis for efficacy will take place after the last subject has finished their Day 42 visit as described in Section 9.1.1.

9.4 Handling of Partial Dates

9.4.1 Investigational Product Administration

If the date of study drug administration is missing, the randomization date will be considered as the date of study drug administration. Line listings will flag any imputed study drug administration dates.

Partial dates or missing time of administration are not possible based on the mandatory fields configured in the eCRF.

9.4.2 Adverse Events and Prior and Concomitant Medications

Dates will not be imputed for Adverse Events or Medical History events. The sites were responsible for imputing start and end dates for TEAEs.

Prior and concomitant medications may have unknown start or end dates. The site makes the determination of whether the medication is a prior or concomitant medication when they enter the medication onto the Prior Medication or Concomitant Medication eCRF page. Partial or unknown dates are not imputed.

Medications entered into the Prior Medication eCRF page with a partial or unknown stop date will be analyzed as both prior and concomitant medications, unless the stop date is a month and/or year combination prior to the study drug administration date.

Subjects exposed to concomitant medications that are scabicides with unknown start dates will be imputed as non-responders, unless the end date of administration is known and is after Day 28.

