9.4.2 Medical History

Medical history will be recorded in the clinic notes and CRF at Screening and include any diagnosed medical conditions and/or current conditions, and significant medical or surgical history. It will include a review of all major body systems including the skin. A detailed history of any previous scabies infestations and treatments will also be collected for each subject.

After Screening, any worsening of Baseline conditions detected during medical history review must be recorded in the subject's clinic notes as well as reported as an AE in the CRF.

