6 STUDY ENDPOINTS

6.1 Primary Efficacy Endpoint

The primary efficacy endpoint is the proportion of index subjects achieving Complete Cure at Day 28. Complete Cure is defined as demonstration of both:

(1) Clinical cure (all signs and symptoms have completely resolved, including burrows, inflammatory/noninflammatory lesions and pruritus).

and

(2) Microscopic or dermatoscopic cure demonstrating the absence of mites, eggs, and/or scybala, and negative dermoscopy for burrows.

Complete Cure will be derived from the individual assessments captured on the Day 28 Scabies Assessment eCRF page where:

- Lesion count is 0, and,
- Pruritus is ‘Absent’, and,
- Mites are ‘Absent’, and,
- Eggs are ‘Absent’, and,
- Scybala are ‘Absent’, and,
- Burrows (by dermoscopy) are ‘Absent’.

An index subject will be considered as having achieved Complete Cure at Day 28 if all of the 6 components are either 0 or “Absent” as specified above. If any of the 6 components are missing, whether because the individual component is missed or because the Day 28 visit was missed, the Complete Cure endpoint at Day 28 will be considered missing and the subject will be imputed as a non-responder (not cured). An exception will be made if the missed visit is non-informative. See Section 9.11.2 for further detail on handling missing data for the Day 28 Complete Cure endpoint.

The Day 28 Complete Cure endpoint for subjects exposed to scabicides prior to their Day 28 assessment will also be imputed as a non-responder (not cured). Scabicides are defined as any scabicide, including permethrin, ivermectin, benzyl benzoate, sulfur, lindane, crotamiton, malathion, tea tree oil, or spinosad used between Day 0 and Day 28. Scabicides do not include products used to manage the symptoms of scabies. Subjects exposed to scabicides as concomitant medications with unknown start dates will also be imputed as non-responders, unless the end date is known and after Day 28.

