7 DEFINITIONS

Terminology	Definitions
Age	Age will be calculated based on the month and year of birth entered in the Demography eCRF page, relative to the month and year of informed consent.
Baseline	The last non-missing assessment immediately prior to exposure to study drug
BMI	Body Mass Index, calculated as $\text{Weight (kg)} / (\text{Height (m)})^2$ (kg/m ²).
Clinical Cure	Demonstration that all signs and symptoms have completely resolved, including burrows, inflammatory/noninflammatory lesions and pruritus.
Complete Cure	Demonstration of both: (1) Clinical cure (all signs and symptoms have completely resolved, including burrows, inflammatory/noninflammatory lesions and pruritus). and

CONFIDENTIAL

Terminology	Definitions
	(2) Microscopic or dermatoscopic cure demonstrating the absence of mites, eggs, and/or scybala, and negative dermoscopy for burrows.
Complete Cure without regard to pruritus	Similar definition as Complete Cure except the pruritus component is not included in the definition, e.g., (1) Clinical cure (all signs and symptoms have completely resolved, including burrows and inflammatory/noninflammatory lesions). and (2) Microscopic or dermatoscopic cure demonstrating the absence of mites, eggs, and/or scybala, and negative dermoscopy for burrows.
Concomitant Medication	Medication taken on the day of or after the first study drug exposure. Concomitant medication may start prior to study drug administration if continued on the day of/after study drug administration.
Dispensing Error	The subject was dispensed less than or more than 16 capsules of moxidectin and/or placebo, but received the assigned treatment
Dosing Error	The subject was dispensed 16 capsules of moxidectin and/or placebo, but did not receive the assigned treatment
Dosing and Dispensing Error	The subject was dispensed less than or more than 16 capsules of moxidectin and/or placebo, and also did not receive the assigned treatment
Investigator Assessed Cure	Investigator selection of one of the three categories below that best describes the cure status of the subject at Day 28: 1. The scabies infestation is clear with all signs resolved, 2. The scabies infestation is clear with incomplete resolution of signs, and no additional treatment with standard of care is warranted, 3. The scabies infestation is not clear and additional treatment with standard of care is warranted.

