As supportive analyses, the Day 28 Complete Cure rates for each moxidectin group and placebo, as well as the risk difference and 95% CIs for each pairwise comparison, will be calculated within each region. For these region subgroup analyses the proportion of index subjects achieving a Day 28 Complete cure for each randomized treatment group within region will be the unadjusted proportions with Wald 95% CIs for a single proportion. The 95% CI for the risk difference will be the Wald CIs for the difference between two independent proportions using the unpooled variance. Any significance test of the risk difference conducted within region will

be viewed as supportive and exploratory due to the potential lack of power. The 95% CIs and any hypothesis tests for these supportive analyses will not be adjusted for multiplicity.

See [Appendix 3](#) for specification of the logistic model and bootstrapping.

9.11.2 Handling of Missing Data for the Primary Analysis of Day 28 Complete Cure

For the Day 28 Complete Cure endpoint, subjects exposed to rescue medication (scabicides, including permethrin, ivermectin, benzyl benzoate, sulfur, lindane, crotamiton, malathion, tea tree oil, or spinosad) prior to the Day 28 assessment will be imputed as a non-responder. If a subject is exposed to a scabicide as a concomitant medication with an unknown start date, they will also be imputed as a non-responder unless the end date is known and is after Day 28. Additionally, subjects with missing Day 28 Complete Cure assessments due to missed visits or incomplete scabies assessments at Day 28 will also be imputed as non-responders. An exception would be if the missing Complete Cure endpoint was missing for reasons deemed as non-informative i.e. the Day 28 visit was missed because weather conditions prevented travel. For the non-informative missing data, the Complete Cure endpoint may be imputed via a fixed value using the methodology detailed in [Appendix 1](#). Should the missing data due to non-informative reasons be greater than 5% of the total sample size (approximately 200 subjects), a multiple imputation approach will be implemented, see [Appendix 2](#).

The determination of the use of rescue medication as well as informative vs non-informative missing data will be conducted prior to the blind break for the Day 42 analysis, see Section [9.6](#).

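### Read literally, the SAP's date rules can score an undated pre-study scabicide as rescue use and overwrite an observed Day 28 cure

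*SAP*

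**What the plan says.** Two rules stand next to each other in SAP 9.4.2.

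- **Double listing.** The site decides whether a drug is prior or concomitant by choosing the eCRF page. Then: "Medications entered into the Prior Medication eCRF page with a partial or unknown stop date will be analyzed as both prior and concomitant medications". The exemption reads "unless the stop date is a month and/or year combination prior to the study drug administration date".
- **Undated scabicides.** "Subjects exposed to concomitant medications that are scabicides with unknown start dates will be imputed as non-responders". The sole exception is for a scabicide with a recorded stop date later than Day 28.

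The second rule is part of the primary endpoint. SAP 6.1 has "Subjects exposed to scabicides as concomitant medications with unknown start dates will also be imputed as non-responders", and SAP 9.11.2 applies the same consequence ("If a subject is exposed to a scabicide as a concomitant medication with an unknown start date"). SAP 9.10 adds a default: where incomplete dates leave the status unclear, the drug counts as concomitant.

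Other parts of the plan point the other way. SAP 6.1 and 7 limit scabicides to those used from Day 0 to Day 28. SAP 7 begins its definition of a concomitant medication with "Medication taken on the day of or after the first study drug exposure". The estimand (SAP 3.4, Protocol 15.6.2) concerns cure without rescue medication. Exclusion criterion 3 (Protocol 8.3) bars scabicides in the 28 days before Screening and between Screening and Baseline, and eligibility is reconfirmed on Day 0 (Protocol 9.3.2, SAP 5.1). Older scabicide use is allowed.

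**The concern.** Past scabies treatment is to be expected in this population, and the protocol asks about it: "A detailed history of any previous scabies infestations and treatments will also be collected for each subject". If such a course is entered on the Prior Medication page without usable dates, the double-listing rule makes it concomitant and the undated-scabicide rule then makes the subject not cured. All six Day 28 components could be clear and the recorded outcome would still be failure.

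The reason for that failure has nothing to do with rescue. The site has recorded the drug as prior and confirmed that no scabicide was used from 28 days before Screening to Baseline. An observed primary outcome would be replaced on the strength of a missing historical date, which lowers cure rates, dilutes the risk difference and departs from the stated estimand. It also leaves room for two programmers to derive different primary outcomes for the same subject.

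**Working it through.** **1. Trace of the rules for a scabicide on the Prior Medication page**

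| Start date | Stop date | After double listing (9.4.2) | After undated-scabicide rule (9.4.2, 6.1, 9.11.2) |
|---|---|---|---|
| Unknown | Wholly unknown | Prior and concomitant | Non-responder |
| Unknown | Year of dosing only | Prior and concomitant | Non-responder |
| Unknown | Month/year or year before dosing | Prior only (exempt) | Not triggered |
| Unknown | Full date before dosing | Prior only | Not triggered |
| Known, before dosing | Unknown | Prior and concomitant | Not triggered; handling not stated |

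Only the first two rows overwrite a cure. A stop date in the same calendar month as dosing is almost excluded for eligible subjects. Exclusion 3 puts the last use at least 29 days before Screening and Screening is at least 1 day before Day 0, so the gap is at least 30 days.

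**2. Whether another planned analysis recovers the observed cure**

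- Complete Analysis Set (SAP 8.5): drops subjects exposed to scabicides before Day 28.
- Per Protocol Analysis Set (SAP 8.4, 9.6): pre-Day 28 scabicide use is a major deviation, so these subjects can be removed.
- Exploratory cure endpoints (SAP 6.3): apply the same non-responder rule.
- Tipping point analysis (SAP 9.11.3.2): switches imputed placebo non-responders only and keeps imputed moxidectin non-responders as failures.

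None uses the observed outcomes in all arms. The listing in SAP 9.11.2 would show the observed value beside the imputed one, so the problem could be seen but would not be corrected.

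**3. The plan's own power figure**

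Inputs from SAP 4: n = 50 per arm, cure 70% against 40%, pooled Z-test, two-tailed alpha 0.019 (z = 2.3455).

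Power = Φ[(d − z·SE0)/SE1], with SE0 = √(2·p̄(1−p̄)/n) and SE1 = √((p1(1−p1) + p0(1−p0))/n).

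- p̄ = 0.55; SE0 = √(0.55 × 0.45 × 0.04) = 0.0995
- SE1 = √((0.21 + 0.24)/50) = 0.0949
- Power = Φ[(0.30 − 2.3455 × 0.0995)/0.0949] = 75.9%, which agrees with the stated 75%.

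**4. Effect if the rule fires**

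Assumption, not in the documents: a share q of subjects in every arm have a qualifying undated entry, unrelated to cure. Cure rates become 0.70(1−q) and 0.40(1−q), so the risk difference is 0.30(1−q).

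| q | Subjects out of 200 | Cure rates | Risk difference | Power |
|---|---|---|---|---|
| 0 | 0 | 70.0% / 40.0% | 30.0 points | 75.9% |
| 1% | 2 | 69.3% / 39.6% | 29.7 | 74.8% |
| 2% | 4 | 68.6% / 39.2% | 29.4 | 73.6% |
| 5% | 10 | 66.5% / 38.0% | 28.5 | 70.2% |

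Past treatment is a pre-randomization feature, so the expected effect is the same in every arm. With no true difference, both arms shrink by the same factor and the difference stays zero.

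Chance imbalance is still possible. At 35/50 against 20/50 the pooled Z-test gives p = 0.0026. If overwritten cures fell only in the moxidectin arm, three would give p = 0.016 (still below 0.019) and four p = 0.028 (no longer significant).

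**The case against.** The best defence is that the double listing is a tabulation convention. SAP 9.10, on medication summaries, uses similar language about reporting continuing drugs in both categories and refers back to 9.4.2. The site decides the category, the definitions in SAP 6.1 and 7 exclude pre-dose use, and rescue use is determined before the Day 42 blind break (SAP 9.11.2). This is a sensible reading and may well be what was meant. It is not written, however. SAP 9.4.2 says analyzed, places the scabicide rule directly afterwards, and gives the blinded review no criterion for undated entries on the Prior Medication page.

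It is also fair that previous scabies treatments may never reach that page. Protocol 9.4.2 collects them as medical history and SAP 9.9 tabulates them there. A site able to confirm exclusion 3 can often supply a month or year before dosing, which is exempt. These points stand and limit the likely frequency.

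A reader might infer more than the text supports in three ways:

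- That any prior scabicide with an undetermined stop date becomes a failure. It does not, because the start date must also be unknown.
- That a substantial share of subjects is affected. No passage supports a particular frequency; even 5% would mean 10 of 200 subjects with undatable scabicides on one eCRF page.
- That the trial's false-positive rate is at risk. The expected effect is equal across arms and works against finding a difference.

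**Conclusion.** The concern holds as a minor conflict within a primary-endpoint rule. Followed literally, the SAP can replace an observed cure with non-response because of a pre-study scabicide that has an unknown start date and a stop date that is unknown or cannot be placed before dosing. That contradicts the SAP's own scabicide definition, the estimand and the eligibility check.

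The size cannot be established from the documents. At assumed frequencies of 1% to 2% the loss is about 1 to 2 power points (74.8% to 73.6%, from 75.9%); at 5% it is about 6 points. These figures assume equal frequency across arms, independence from cure, and the planning rates of 70% and 40%. No type I error inflation is expected.

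**What to change.** In SAP 9.4.2, 6.1 and 9.11.2, state two things:

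- Listing a Prior Medication entry as both prior and concomitant is for medication summaries only.
- The non-responder rule for scabicides with unknown start dates applies only to entries on the Concomitant Medication page. A scabicide entered as prior is not rescue unless the blinded review before the Day 42 blind break documents use on or after Day 0.

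The cost is about one sentence in each of the three sections and a short blinded check of scabicide entries on the Prior Medication page. The check fits within the rescue determination that SAP 9.11.2 already requires before the blind break.

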9.5 Subject Disposition

The subject disposition summary will present the number (%) of subjects (as appropriate) who were:

- Screened (Number [N] only)
 - Screen Failures (n, % N Screened)
 - Reason for screen failure: not meeting eligibility criteria by eligibility criterion (n, % N Screen Failures)
- All Randomized (% N Screened)
 - No exposure to study drug (n, % N All Randomized)
 - Exposed to study drug (n, % N All Randomized)
 - Full analysis set (n, % N All Randomized)
 - Per protocol analysis set (n, % N All Randomized)
 - Complete analysis set (n, % N All Randomized)
 - Safety analysis set (n, % N All Randomized)
 - PK Analysis Set (n, % N All Randomized)
 - Day 42 Completers (Day 42 summary only, n, % N All Randomized)
 - Subjects who prematurely discontinued the study prior to the Day 42 visit (Day 42 summary only, n, % N All Randomized)
 - Reasons for discontinuation prior to the Day 42 visit (Day 42 summary only, n, % N subjects who discontinued)
 - Week 16 Completers (Week 16 summary only, n, % N All Randomized)
 - Subjects who prematurely discontinued the study prior to the Week 16 visit (Week 16 summary only, n, % N All Randomized)
 - Reasons for discontinuation prior to the Week 16 visit (Week 16 summary only, n, % N subjects who discontinued)
 - Last scheduled assessment (Day 42 and Week 16 summaries, n, % N All Randomized)

Percent calculations with "N All Randomized" as the denominator will be calculated by randomized treatment group and overall. Subject disposition data will be presented in line listings. Subjects in the All Randomized set will be included in the disposition line listings.

9.6 Protocol Deviations

A blinded review of protocol deviations documented during the study will be completed prior to the database freeze/lock and blind break for the Day 42 analysis. Protocol deviations are categorized at the time of entry into the Protocol Deviation eCRF page, but categorization will be reviewed during blinded review of all protocol deviations, and they will also be classified as major/minor:

- Consent procedures
- Inclusion/exclusion criteria
- Randomization procedures

- Concomitant medication/therapy
- Study procedures
- Serious adverse event (SAE) reporting
- Dosing
- Unblinding
- Scabies Assessment outside the Day 28 Visit Window
- Other Visit schedule/ interval
- COVID-19 related
- Other

Major protocol deviations will be defined as deviations that could potentially have a meaningful impact on the efficacy or safety results. Subjects with major protocol deviations that might impact efficacy will be excluded from the PPAS.

Some categories of major protocol deviations that might be considered as having a meaningful impact on the efficacy results include but are not limited to:

- Subjects failing any eligibility criteria,
- Subjects with treatment administration errors,
- Subjects randomized but not exposed to study drug (exclusion from FAS, PPAS, SfAS), and PK,
- Significant non-compliance with specified study visits windows,
- Administration of scabicides prior to the Day 28 visit (note: the exposure to scabicides prior to Day 28 is considered a major protocol deviation and subjects will be considered non-responders for the primary analysis)

Protocol deviations leading to missing data will also be reviewed to assess the reasons why the data are missing and whether they are considered informative or non-informative reasons for the purposes of handling of missing data described in Section 9.11.2. Where the reason(s) for missing data is unknown and/or not fully documented, the default will be to assume informative missing. Examples of non-informative missing data might be:

- Missed visit due to weather, travel, or childcare,
- Missed visit due to COVID-19 or COVID-19 exposure,
- Missed assessment due to equipment failure.

All determinations of informative and non-informative missing data will be fully documented and reported.

Prior to the Week 16 analysis, another blinded review will be conducted to assign deviations to the same categories listed above for deviations that occurred after Day 42 during the Extended Safety Follow Up period. Although unlikely, it is possible that a protocol deviation, or another issue, that might impact the final efficacy analysis conducted earlier at the Day 42 analysis, is discovered during the protocol deviation review of data collected during the extended safety

follow up. Should this be the case, the Sponsor will describe the error, the circumstances of the discovery, and an assessment of what impact, if any, it might have on the interpretation or conclusion of the final Day 28 efficacy analyses.

Summary tables describing the number and percent of subjects in each protocol deviation category for major deviations will be tabulated by randomized treatment group for all randomized subjects regardless of exposure to study drug. Subjects may be included in more than one category. If a major protocol deviation trend is identified in the 'Other' category and cannot be classified in an already identified category above, then an additional category will be defined at the time of analysis. All protocol deviations will be provided in line listings and include their category and major/minor classification.

